9.2.3. Adverse Event Summaries

An overall summary of AEs by treatment group will include:

- Number (%) of participants reporting any TEAEs
- Number (%) of participants reporting any serious TEAEs
- Number (%) of participants reporting any Grade 3 or higher TEAEs
- Number (%) of participants reporting any treatment-related TEAEs
- Number (%) of participants who temporarily interrupted study drug because of TEAEs
- Number (%) of participants who permanently discontinued study drug because of TEAEs
- Number (%) of participants who had a fatal TEAE

The following summaries will be produced by MedDRA term (if 5 or fewer participants appear in a table, a listing may be appropriate):

- Summary of TEAEs by SOC and PT
- Summary of TEAEs by PT in decreasing order of frequency
- Summary of Grade 3 or higher TEAEs by SOC and PT
- Summary of Grade 3 or higher TEAEs by PT in decreasing order of frequency
- Summary of serious TEAEs by SOC and PT
- Summary of serious TEAEs by PT in decreasing order of frequency
- Summary of ASRs by SOC and PT

CONFIDENTIAL

- Summary of ASRs by PT in decreasing order of frequency
- Summary of treatment-related TEAEs by SOC and PT
- Summary of treatment-related TEAEs by PT in decreasing order of frequency
- Summary of Grade 3 or higher treatment-related TEAEs by SOC and PT
- Summary of treatment-related serious TEAEs by SOC and PT
- Summary of TEAEs with a fatal outcome by SOC and PT
- Summary of TEAEs leading to dose interruption of study drug by SOC and PT
- Summary of TEAEs leading to discontinuation of study drug by SOC and PT

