The skin of patients with vitiligo is characterized by depigmented patches that result from the infiltration of affected areas with activated antigen-specific CD8+T cells that drive melanocyte death and disease pathogenesis (Taïeb and Picardo 2009, van den Boorn et al 2009). Recruitment of autoreactive CD8⁺ T cells to melanocytes is mediated by IFN- γ through the IFN- γ -induced chemokines CXCL9 and CXCL10, a signaling pathway regulated by JAK1 and JAK2 (Harris et al 2012, Rashighi et al 2014, Rashighi and Harris 2015). The interruption of IFN- γ signaling via the JAK pathway represents an important therapeutic strategy to evaluate in the treatment of vitiligo (Dina et al 2019). In a recent randomized, double-blind, placebo-controlled Phase 2 study (INCB 18424-211; NCT03099304), ruxolitinib cream, a topical JAK1/2 inhibitor, demonstrated efficacy in patients with vitiligo (Rosmarin et al 2020; see also Section 2.2.2 for a brief summary of findings from this study). The specific impacts of ruxolitinib cream on the biology of melanocytes were not evaluated in this study, but the findings warrant an evaluation of the effects of ruxolitinib cream on melanocytes and support continued clinical development of ruxolitinib cream for the treatment of patients with vitiligo.

Safety findings from this Phase 2 study and 2 ongoing Phase 3 studies (INCB 18424-306 and INCB 18424-307) in participants with vitiligo also support continued development of ruxolitinib cream for the treatment of patients with this condition. As of the cutoff date for the ruxolitinib cream IB (Edition 9), a total of 203 participants with vitiligo have received ruxolitinib cream.

Safety findings across the 3 vitiligo studies showed that the majority of participants had good local tolerability with use of ruxolitinib cream, there were few application site reactions (all Grade 1 or 2), and all SAEs were reported in 1 participant each (ie, there were no patterns of SAEs).

Refer to the ruxolitinib cream IB for a summary of available clinical efficacy and safety data from the vitiligo studies as well as safety data from ruxolitinib cream clinical studies conducted in other disease states.

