10.5.5. Safety Analysis

Safety is being evaluated as a secondary objective in this study. Safety analyses will be conducted using the safety population and are summarized in Table 10.

Table 10:Safety Analyses

Objective	Statistical Analysis Methods	
To assess the safety and local tolerability of ruxolitinib cream.	Adverse Events A TEAE is any AE either reported for the first time or worsening of a pre-existing event	
	after first dose of study drug. Analysis of AEs will be limited to TEAEs, but data listings will include all AEs regardless of their timing to study drug administration. Adverse events will be coded using MedDRA and tabulated by preferred term and system organ class. Severity of AEs will be based on the CTCAE v5.0 using Grades 1 through 5.	
	The subset of AEs considered by the investigator to have a relationship to study drug will be considered to be treatment-related AEs. If the investigator does not specify the relationship of the AE to study drug, then the AE will be considered treatment-related. The incidence of AEs and treatment-related AEs will be tabulated.	
	Clinical Laboratory Tests	
	Actual values and changes from baseline in clinical laboratory test results will be summarized using descriptive statistics. Laboratory test values outside the normal range will be assessed for severity based on the normal ranges for the clinical reference laboratory. The incidence of abnormal laboratory values will be tabulated.	
	Laboratory data will be classified into Grades 1 through 5 using CTCAE v5.0. The following summaries will be produced for the laboratory data:	
	• Number and percentage of participants with worst postbaseline CTCAE grade (regardless of baseline value). Each participant will be counted only for the worst grade observed postbaseline.	
	• Shift tables from baseline to the worst postbaseline value using CTCAE grade.	
	• For laboratory parameters where CTCAE grades are not defined, shift tables to the worst postbaseline value using the low/normal/high classifications based on laboratory reference ranges.	
	Vital Signs	
	Descriptive statistics and mean change from baseline will be determined for vital signs (blood pressure, pulse, respiratory rate, and body temperature) at each assessment time.	
	Electrocardiograms	
	Descriptive statistics and mean change from baseline will be determined for each ECG parameter at each assessment time.	

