2.2. Study Objectives and Endpoints

Table 1 presents the objectives and endpoints.

Table 1:Objectives and Endpoints

Objectives	Endpoints
Primary	
To evaluate the change in immune biomarkers in participants with vitiligo.	Percentage change from baseline in immune biomarkers, including CXCL10, at Week 4, Week 12, and Week 24.
Secondary	
To correlate the change in key serum and skin biomarkers of vitiligo to efficacy.	Correlation of key skin inflammatory biomarkers of vitiligo in target lesions to efficacy readouts at Week 12 and Week 24.
To assess the safety and local tolerability of ruxolitinib cream.	The frequency and severity of AEs.

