9.2. Adverse Events

9.2.1. Adverse Event Definitions

A TEAE is any AE either reported for the first time or worsening of a pre-existing event after the first application of study drug and within 30 days of the last application of study drug. For participants who cross over treatments, the first application date is period-specific, and the end date is 30 days after the last application date in the period, or the day before the first application date in the next period, whichever comes first. Analysis of AEs (as discussed below) will be limited to TEAEs, but data listings will include all AEs regardless of their timing in relation to study drug application.

Adverse events will be tabulated by MedDRA PT and SOC. Severity of AEs will be graded using the NCI CTCAE v5.0. The CTCAE reporting guidelines and grading details are available on the Cancer Therapy Evaluation Program website.

The subset of AEs considered by the investigator to be related to study drug will be considered to be treatment-related AEs. If the investigator does not specify the relationship of the AE to study drug, the AE will be considered to be treatment-related. The incidence of AEs and treatment-related AEs will be tabulated. Serious AEs will also be tabulated.

Any missing onset date, causality, or severity must be queried for resolution. Unresolved missing causality and severity will be handled according to the following rules:

- An unresolved missing causality will be considered treatment-related.
- An unresolved missing severity will be identified as an unknown severity.

For purposes of analysis, all AEs will be considered TEAEs unless the AE can unequivocally be defined as not treatment-emergent.

Application site reactions are AEs that occur at the site of study drug application. A summary of ASRs will be provided. Exposure-adjusted summaries will be provided for the safety population including cumulative TEAEs.

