3.2.3.1.X	Summary of Treatment-Emergent Adverse Events by MedDRA Preferred Term in Decreasing Order of Frequency	Safety/TEE
3.2.3.1.2.X	Summary of Application Site Reactions by MedDRA System Organ Class and Preferred Term	Safety/TEE
3.2.3.1.3.X	Summary of Application Site Reactions by MedDRA Preferred Term in Decreasing Order of Frequency	Safety/TEE
3.2.3.1.Y	Summary of Treatment-Emergent Adverse Events With Vehicle Group by MedDRA Preferred Term in Decreasing Order of Frequency During the Treatment Period	Safety
3.2.3.1.2.Y	Summary of Application Site Reactions With Vehicle Group by MedDRA Preferred Term in Decreasing Order of Frequency During the Treatment Period	Safety
3.2.3.1.3.Y	Summary of Exposure-Adjusted Incidence Rates of Treatment-Emergent Adverse Events With Vehicle Group by MedDRA Preferred Terms in Decreasing Order of Frequency During the Treatment Period	Safety
3.2.3.1.5.Y	Summary of Exposure-Adjusted Incidence Rates of Application Site Reactions With Vehicle Group by MedDRA Preferred Term in Decreasing Order of Frequency During the Treatment Period	Safety
3.2.4.1.X	Summary of Grade 3 or Higher Treatment-Emergent Adverse Events by MedDRA System Organ Class and Preferred Term	Safety/TEE
3.2.4.2.X	Summary of Grade 3 or Higher Treatment-Emergent Adverse Events by MedDRA Preferred Term in Decreasing Order of Frequency	Safety/TEE
3.2.5.1.X	Summary of Serious Treatment-Emergent Adverse Events by MedDRA System Organ Class and Preferred Term	Safety/TEE
3.2.5.2.X	Summary of Serious Treatment-Emergent Adverse Events by MedDRA Preferred Term in Decreasing Order of Frequency	Safety/TEE
3.2.6.1.X	Summary of Treatment-Related Treatment-Emergent Adverse Events by MedDRA System Organ Class and Preferred Term	Safety/TEE
3.2.6.2.X	Summary of Treatment-Related Treatment-Emergent Adverse Events by MedDRA Preferred Term in Decreasing Order of Frequency	Safety/TEE
3.2.7.1.X	Summary of Grade 3 or Higher Treatment-Related Treatment-Emergent Adverse Events by MedDRA System Organ Class and Preferred Term	Safety/TEE

Table No.	Title	Population
3.2.8.1.X	Summary of Treatment-Related Serious Treatment-Emergent Adverse Events by MedDRA System Organ Class and Preferred Term	Safety/TEE
3.2.9.1.X	Summary of Treatment-Emergent Adverse Events With a Fatal Outcome by MedDRA System Organ Class and Preferred Term	Safety/TEE
3.2.10.1.X	Summary of Treatment-Emergent Adverse Events Leading to Dose Interruption of Study Drug by MedDRA System Organ Class and Preferred Term	Safety/TEE

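### AE severity is a named secondary endpoint, but the visible summary tables cut grade only at Grade 3 or higher (plus fatal events), and no application site reaction table title mentions grade

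*SAP*

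**What the plan says.** SAP 2.2 (Table 1) sets the secondary objective "To assess the safety and local tolerability of ruxolitinib cream" and gives it one endpoint: "The frequency and severity of AEs". Protocol Section 3 has the same pair.

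Severity is collected on a full scale. Protocol 10.5.5 states "Severity of AEs will be based on the CTCAE v5.0 using Grades 1 through 5", and SAP 9.2.1 states "Severity of AEs will be graded using the NCI CTCAE v5.0". SAP 9.2.1 also sets aside an unknown category for grades that stay missing after query.

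The summaries are listed in SAP 9.2.3. The overall table includes "Number (%) of participants reporting any Grade 3 or higher TEAEs". The MedDRA summaries include Grade 3 or higher TEAEs, Grade 3 or higher treatment-related TEAEs and fatal TEAEs. Application site reactions (ASRs) appear as "Summary of ASRs by SOC and PT" and by PT in order of frequency. Appendix A follows the same pattern, for example "Summary of Application Site Reactions by MedDRA System Organ Class and Preferred Term".

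On what to expect, Protocol 2.1 says of the three vitiligo studies that "there were few application site reactions (all Grade 1 or 2" were seen, and that most participants tolerated the cream well locally.

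**The concern.** For a cream compared with its own vehicle, local tolerability depends largely on how bothersome mild and moderate skin reactions are. On the protocol's fallback scale (Protocol 9.3), Grade 1 means treatment is not indicated, while Grade 2 means some local or minimal treatment and some limit on daily activities. If reactions again stay within those two grades, a Grade 3 cut cannot separate them. Two arms with the same participants reacting and the same PTs, one all Grade 1 and the other all Grade 2, would give the same ASR tables. A reader of the study report could compare how often local reactions occurred in each arm, but not how severe they were, although severity is part of the endpoint.

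**Working it through.** The plan states no figure on this point, so the check is a count of the displays, followed by one illustration.

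**Count of visible summary displays**

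| Place | Displays | Grade 3 or higher | Fatal | Any split below Grade 3 |
|---|---|---|---|---|
| SAP 9.2.3, overall AE summary | 7 lines | 1 | 1 | 0 |
| SAP 9.2.3, MedDRA summaries | 15 | 3 | 1 | 0 |
| Appendix A, AE table titles | 21 | 3 (3.2.4.1.X, 3.2.4.2.X, 3.2.7.1.X) | 1 (3.2.9.1.X) | 0 |
| Of those 21, ASR titles | 4 (3.2.3.1.2.X, 3.2.3.1.3.X, 3.2.3.1.2.Y, 3.2.3.1.5.Y) | 0 | 0 | 0 |

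**Three comparisons within the documents**

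- SAP 9.3.2 plans a worst post-baseline grade summary for laboratory values, with each participant counted once. AEs, which carry the endpoint, have no visible counterpart.
- SAP 9.2.1 defines an unknown severity category, but no visible summary is arranged by severity, so that category has no place to appear.
- Protocol 9.3 has each change in severity recorded as a separate AE. A per-participant severity summary therefore needs a worst-grade rule, and none is visible for AEs.

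**How often would a Grade 3 cut pick up a local reaction?** This is an illustration only. Assume that none of the 203 vitiligo participants exposed to the cream (Protocol 2.1) had a Grade 3 or higher ASR. With zero events in n = 203, the exact upper limit for the true rate p solves (1 − p)^203 = a, so p = 1 − a^(1/203).

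- One-sided 95%: p = 1 − 0.05^(1/203) = 0.0146, about 1.5%.
- Two-sided 95%: p = 1 − 0.025^(1/203) = 0.0180, or 1.8%.

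The ruxolitinib arm has about 40 participants (SAP Figure 1). The expected number with such a reaction is 40p, and the chance of at least one is 1 − (1 − p)^40:

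| True rate p | Expected in 40 | Chance of at least one |
|---|---|---|
| 0.25% | 0.10 | 9.5% |
| 0.5% | 0.20 | 18.2% |
| 1.0% | 0.40 | 33.1% |
| 1.46% (one-sided limit) | 0.59 | 44.6% |
| 1.80% (two-sided limit) | 0.72 | 51.7% |

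Even at the upper limits, fewer than one such participant is expected. The Grade 3 tables are therefore likely to say little or nothing about local reactions.

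**The case against.** The strongest points on the other side are these.

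- **Severity is tabulated.** Grade 3 or higher and fatal TEAEs have their own tables, and a Grade 3 or higher local reaction would show there by PT. Interruption and discontinuation tables add indirect information. This stands. A reader might infer that the endpoint is delivered for frequency only; the documents do not support that.
- **No by-grade table was promised.** The endpoint does not prescribe a display, and Protocol 10.5.5 commits only to grading AEs and tabulating their incidence. This also stands: the SAP breaks no protocol commitment. The gap lies in how informative the tables are for the stated endpoint.
- **Listings may cover it.** Listings 2.7.1 (all AEs) and 2.7.9 (ASRs) are planned. SAP 9.1 and 9.2.3 let a listing stand in for a sparse table (five or fewer participants in 9.2.3). With few ASRs, grades could be compared by hand. This stands in part: the layouts are not shown, nothing says that Listing 2.7.9 carries grade, and it does not help for TEAEs overall.
- **Absence cannot be proved.** Section 9.2.2 is not in the public text, Table 3.2.3.1.4.Y and Listing 2.7.7 are skipped in the numbering, and the Standard Safety Tables v1.12 and sample displays are separate documents. A standard shell may already have grade columns. This stands and limits confidence, although the visible list in 9.2.3 has no evident gap and agrees with Appendix A.
- **The stakes are small.** This is an exploratory study with no alpha control, and about 20 vehicle participants with few reactions may show little. That is fair. It affects the weight of the point but does not argue against a descriptive table.

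**Conclusion.** The point holds in a limited form. In the visible plan, AE severity is summarised only at Grade 3 or higher and as fatal events, with 0 of 21 AE table titles splitting grades below 3 and 0 of 4 ASR titles mentioning grade. If local reactions again stay at Grades 1 and 2, the planned summary tables would not compare the arms on their severity, and grade would be available only in participant-level listings whose layouts are not shown.

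It would go too far to say that severity is wholly unanalysed. Grades are collected, and severe and fatal events are tabulated.

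The conclusion rests on the visible lists being complete and on earlier experience repeating itself. The display count does not depend on the 203-participant illustration. That illustration is only an assumption, partly because two of the three studies were ongoing. The documents give no ASR counts by grade, so the size of any Grade 1 versus Grade 2 difference cannot be estimated. No estimate or decision rule in the trial depends on it. This is an inexpensive improvement to the displays.

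**What to change.** In SAP 9.2.3 and Appendix A, add the following by treatment group, for the double-blind period (safety population) and the extension period (TEE population):

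- (a) TEAEs by SOC, PT and maximum CTCAE grade (1, 2, 3 or higher, unknown), counting each participant once at the worst grade within each row. State this rule explicitly, because each severity change is recorded as a separate AE.
- (b) ASRs by PT and maximum grade, under the same rule.

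If ASRs turn out to be too few for a table, state in the SAP that Listing 2.7.9 shows grade and treatment group. If the standard shells already include these tables, name them in 9.2.3; nothing more is then needed.

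The cost is two descriptive tables in each of two periods, 2 × 2 = 4 in all. No new data, test or sample size change is required. Appendix A already allows changes to its lists without an SAP amendment when the nature of the analysis is unaffected, although the worst-grade rule belongs in the text of 9.2.3.

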9.3. Clinical Laboratory Tests

9.3.1. Laboratory Value Definitions

All laboratory assessments will be performed using a central laboratory except for urine pregnancy tests (as applicable). Laboratory values and change from baseline values will be summarized descriptively by visit, and non-numeric test values will be tabulated when necessary.

The baseline value will be determined using the last nonmissing value collected before the first application, prioritizing scheduled assessments for baseline identification over unscheduled visits. The last record before application in the highest priority will be considered the baseline record. For baseline laboratory candidates with the same date and time in the same priority category, additional rules may be provided after consultation with the medical monitor to delineate which value will be defined as baseline.

9.3.2. Laboratory Value Summaries

Actual values and changes from baseline in clinical laboratory test results will be summarized using descriptive statistics. Laboratory test values outside the normal range will be assessed for severity based on the normal ranges for the clinical reference laboratory. The incidence of abnormal laboratory values will be tabulated.

Laboratory data will be classified into Grades 1 through 5 using CTCAE v5.0. The following summaries will be produced for the laboratory data:

- Number and percentage of participants with worst postbaseline CTCAE grade (regardless of baseline value). Each participant will be counted only for the worst grade observed postbaseline.
- Shift tables from baseline to the worst postbaseline value using CTCAE grade.
- For laboratory parameters where CTCAE grades are not defined, shift tables to the worst postbaseline value using the low/normal/high classifications based on laboratory reference ranges.

10. VITAL SIGNS

Values at each scheduled visit, change, and percentage change from baseline for vital signs, including systolic blood pressure, diastolic blood pressure, pulse, temperature, and respiratory rate, will be summarized descriptively.

Normal ranges for vital sign values are defined in Table 2. For participants exhibiting vital sign abnormalities, the abnormal values will be listed along with their assigned treatment group. Alert vital signs are defined as an absolute value outside the defined normal range and percentage change > 25%. The abnormal values for participants exhibiting alert vital sign abnormalities will be listed.

Parameter	Low Threshold	High Threshold	
Systolic blood pressure	\geq 85 mmHg	≤ 155 mmHg	
Diastolic blood pressure	\geq 40 mmHg	$\leq 100 \text{ mmHg}$	
Pulse	\geq 45 bpm	$\leq 100 \text{ bpm}$	
Temperature	≥ 35.5°C	≤ 38°C	
Respiratory rate	\geq 8 breaths/min	\leq 24 breaths/min	

Table 2:Normal Ranges for Vital Sign Values

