8.3.3. Vital Signs

Vital sign measurements will be taken at all visits.

Vital sign measurements include blood pressure, pulse, respiratory rate, and body temperature. Blood pressure and pulse will be taken with the participant in the recumbent, semirecumbent, or sitting position after 5 minutes of rest. Any abnormalities that are considered clinically significant in the judgment of the investigator are to be reported as AEs.

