4.1.3. Baseline Value

Baseline is the last nonmissing measurement obtained before the first application of ruxolitinib cream or vehicle cream in the double-blind period.

For randomized participants not treated with any study drug, baseline is defined as the last nonmissing assessment before randomization for all parameters.

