3.2.11.1.X	Summary of Treatment-Emergent Adverse Events Leading to Discontinuation of Study Drug by MedDRA System Organ Class and Preferred Term	Safety/TEE
Laboratory values and vital signs		
3.3.1.X	Summary of Laboratory Values – Hematology	Safety/TEE
3.3.3.X	Shift Summary of Hematology Laboratory Values in CTCAE Grade – To the Worst Abnormal Value	Safety/TEE
3.3.4.X	Summary of Laboratory Values – Chemistry	Safety/TEE
3.3.6.X	Shift Summary of Chemistry Laboratory Values in CTCAE Grade – To the Worst Abnormal Value	Safety/TEE
3.4.1.X	Summary of Systolic Blood Pressure	Safety/TEE
3.4.2.X	Summary of Diastolic Blood Pressure	Safety/TEE
3.4.3.X	Summary of Pulse	Safety/TEE
3.4.4.X	Summary of Respiration Rate	Safety/TEE
3.4.5.X	Summary of Body Temperature	Safety/TEE

Note: For AE tables ending with X, separate tables will be provided for the double-blind period (safety population) and treatment extension period (TEE population).

Note: For AE tables ending with Y, tables will be provided for the overall treatment period (double-blind and treatment extension periods). Participants who cross over should be included in both treatment groups.

Note: For laboratory values/vital sign tables ending with X, separate tables will be provided for the double-blind period (safety population) and treatment extension period (TEE population).

Listings

Listing No.	Title		
Demographic and baseline characteristics			
2.1.1	Participant Enrollment and Disposition Status		
2.1.2	Participants Who Discontinued Treatment or Discontinued From Study Due to COVID-19		
2.1.3	Participants With Assessments Not Done Due to COVID-19 Pandemic		
2.2.1	Protocol Deviations		
2.2.2	Participant Inclusion and Exclusion Criteria Violations		
2.3	Analysis Populations		
2.4.1	Demographic Characteristics		
2.4.2	Baseline Disease Characteristics		
2.4.3	Medical History		
2.4.4	Prior and Concomitant Medications		
2.4.5	Prior Medications for Vitiligo		
2.5.1	Study Drug Exposure and Compliance		
-			
-			
Adverse even	ts		
2.7.1	Adverse Events		
2.7.2	Adverse Events Leading to Study Drug Discontinuation		
2.7.3	Serious Adverse Events		
2.7.4	Treatment-Related Adverse Events		
2.7.5	Adverse Events With a Fatal Outcome		
2.7.6	Adverse Events Leading to Interruption of Study Drug		
2.7.8	Grade 3 or Higher Adverse Events		
2.7.9	Application Site Reactions		
Laboratory d	lata		
2.8.1.1	Clinical Laboratory Values – Hematology		
2.8.1.2	Clinical Laboratory Values – Chemistry		

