2.8.1.3	Abnormal Clinical Laboratory Values – Hematology		
2.8.1.4	Abnormal Clinical Laboratory Values – Chemistry		
Vital signs			
2.8.2.1	Vital Signs		
2.8.2.2	Abnormal Vital Sign Values		
2.8.2.3	Alert Vital Sign Values

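### Does it matter that the SAP's alert rule for vital signs can hardly ever flag a body temperature?

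*SAP*

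**What the plan says.** SAP Section 10 plans descriptive summaries of values, change and "percentage change from baseline for vital signs, including systolic blood pressure, diastolic blood pressure, pulse, temperature, and respiratory rate". Its Table 2 gives a normal range for each of the five; for temperature it is 35.5 to 38°C.

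Two listings then follow from two rules.

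- **Range only.** "For participants exhibiting vital sign abnormalities, the abnormal values will be listed along with their assigned treatment group". In Appendix A this is Listing 2.8.2.2, "Abnormal Vital Sign Values".
- **Range and change.** "Alert vital signs are defined as an absolute value outside the defined normal range and percentage change > 25" per cent. In Appendix A this is Listing 2.8.2.3, "Alert Vital Sign Values".

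Neither Section 10 nor Appendix A exempts temperature from the second rule or gives it a criterion based on degrees. The reference value is set in SAP Section 4.1.3: "Baseline is the last nonmissing measurement obtained before the first application of ruxolitinib cream or vehicle cream in the double-blind period".

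Appendix A also plans a full vital-signs listing (2.8.2.1) and Table 3.4.5.X, "Summary of Body Temperature". Protocol Section 8.3.3 adds: "Any abnormalities that are considered clinically significant in the judgment of the investigator are to be reported as AEs".

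**The concern.** A relative-change threshold suits variables that can move by a quarter of their value. Blood pressure, pulse and respiratory rate can do so; body temperature in degrees Celsius cannot. Because the two conditions are joined by *and*, a high fever would not qualify as an alert.

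The listing would then show no temperature rows whether or not notable fevers had occurred, and a reader could take the blank as reassurance. Protocol Section 2.3 names an increased rate of infection as a potential risk of immunomodulation, so a safety reader might well look for fever under the heading of alert values.

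**Working it through.** **Inputs.** Limits from SAP Table 2; the 25% from SAP Section 10; baseline as in SAP Section 4.1.3. The alert sentence does not repeat that the change is from baseline, but that is the only percentage change the section defines. The plan states no figure to reproduce here.

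**Formulas.** Write b for baseline, L and U for the lower and upper limits, v for the reading.

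- High alert: v > U and v > 1.25 × b.
- Low alert, if the 25% means change in either direction: v < L and v < 0.75 × b.

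**Temperature from an in-range baseline.**

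| Baseline (°C) | High alert needs more than | Low alert needs less than |
|---|---|---|
| 35.5 | 1.25 × 35.5 = 44.4 | 0.75 × 35.5 = 26.6 |
| 37 | 1.25 × 37 = 46.25 | 0.75 × 37 = 27.75 |
| 38 | 1.25 × 38 = 47.5 | 0.75 × 38 = 28.5 |

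For scale, going from 35.5 to 38°C is (38 − 35.5)/35.5 = 7.0%, and from 37 to 40°C is 3/37 = 8.1%.

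A moderately abnormal baseline does not help: from 34°C the reading must exceed 1.25 × 34 = 42.5°C, and from 39°C it must fall below 0.75 × 39 = 29.25°C. Recording in Fahrenheit does not help either: from 98.6°F (37°C) the high alert needs more than 1.25 × 98.6 = 123.25°F, which is 50.7°C.

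**Is this specific to temperature?** The test is whether some in-range baseline exists from which merely leaving the range is already a change of more than 25%. On the high side that holds for baselines up to U/1.25; on the low side, for baselines from L/0.75 upwards.

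| Parameter | Table 2 range | U/1.25 | L/0.75 | Both inside the range? |
|---|---|---|---|---|
| Systolic (mmHg) | 85 to 155 | 124 | 113.3 | Yes |
| Diastolic (mmHg) | 40 to 100 | 80 | 53.3 | Yes |
| Pulse (bpm) | 45 to 100 | 80 | 60 | Yes |
| Respiratory rate (per min) | 8 to 24 | 19.2 | 10.7 | Yes |
| Temperature (°C) | 35.5 to 38 | 30.4 | 47.3 | No, neither |

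Only temperature fails. The low-side column again assumes that falls count. On a strictly signed reading, no fall from an in-range baseline could be an alert for any of the five.

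**Where an out-of-range temperature would appear.** Take a reading of 40°C from a baseline of 37°C.

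- Listing 2.8.2.1: the title carries no abnormality filter, so it should appear.
- Listing 2.8.2.2: yes, since 40 exceeds 38, and it is shown with treatment group.
- Table 3.4.5.X: yes, as part of the visit summaries.
- Adverse-event tables: yes, if the investigator judges it clinically significant.
- Listing 2.8.2.3: no, since 8.1% is below 25%.

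Four of the five outputs can carry it, and the one that cannot is a stricter subset of Listing 2.8.2.2.

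**The case for a change.** The best case for a change is that the rule visibly does not work for one of the five parameters it covers. A template origin would explain this without making the rule work. The remedy is also tiny: one sentence and one footnote saying that the alert rule does not apply to temperature and pointing to Listing 2.8.2.2. It adds no threshold and touches no test.

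The arithmetic behind this stands in full. The consequence does not. The reader is misled only by taking Listing 2.8.2.3 alone. Listing 2.8.2.2 comes directly before it and settles the matter: temperature rows there mean out-of-range temperatures occurred, and no such rows mean none did. The rule itself is printed in SAP Section 10 for anyone who wonders why the alert listing is silent.

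The footnote may also exist already. SAP Sections 6 and 9 place the sample displays in a separate document that is not available here. As for removing the 25% condition for temperature, that would copy rows from one listing into the next.

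The missing direction of the 25% is a small gap of its own. Reading it as change in either direction is the sensible choice, because Table 2 sets low as well as high limits, and an analyst would be expected to program it that way. The finding for temperature is the same on either reading.

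**Conclusion.** The observation is correct and has no practical effect. From an in-range baseline, a temperature alert needs more than 44.4 to 47.5°C or less than 26.6 to 28.5°C. In practice, only a data-entry or unit error would be expected to produce one.

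No change to the plan follows, because none would gain anything. Every out-of-range temperature is already listed by treatment group without the 25% condition, temperature is summarized, and clinically significant abnormalities reach the adverse-event analysis. The cost is one listing that is uninformative about one parameter when read in isolation, which is a tolerable by-product of using a single rule for five variables. No endpoint, comparison or safety conclusion depends on it.

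This rests on three assumptions. The 25% is measured from baseline, as the rest of Section 10 implies. It covers falls as well as rises, which matters only for the low-side figures. And participants at study visits do not reach the alert temperatures, which is general physiology and not a figure from the documents.
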